## 2.4 Ethical considerations

The study will be conducted in full accordance with the Declaration of Helsinki, the German data protection act, and the GCP-Guideline and is sensitive to ethical considerations. The study protocol, amendments to the protocol (if applicable), therapy contents, patient recruitment procedures, information and informed consent form will be presented to the TUD ethics committee for approval. Subsequently, the study protocol will be approved by the respective site's ethics committees.

## 2.5 Quality assurance and safety

### 2.5.1 Quality assurance and monitoring

All participating centers are highly experienced with multicenter quality assurance and management procedures specified in SOPs and used in this RCT. All staff will be trained by CELOS and KKS Dresden and will go through three 2 days training sessions for (i) assessment, (ii) the treatment manual and (iii) general procedures of data entry, quality assurance and data management using web-based system MACRO. Subsequently there will be a 2 week site implementation phase, in which the coordinating center staff will visit and monitor the site personnel (month 4). Prior to the start there will be a third 2-days training to assess reliability

for assessment instruments and final adjustment in procedures (linkages to associated projects). All sites are requested to monitor all assessment and treatment sessions by tapes. Tapes will be randomly (5%) checked by the coordinating center to detect protocol violations as soon as possible. 1-day booster training sessions for assessment and the manual will be conducted every 3 months.

## **3. Add-on project Psychophysiology (P3): Behavioral and psychophysiological markers of extinction learning and outcome**

### **3.1 Background and aims**

The most effective treatment of anxiety disorders share exposure techniques as a core ingredient. Exposure treatment needs to be tailored in a way to promote extinction learning and prevent return of fear. The current research proposal aims to investigate the process of extinction learning across a large group of anxiety disorder (AD) patients prior to and after exposure therapy. We want to assess extinction learning at all levels of the emotional network, including verbal report (US-expectancy ratings), physiological arousal (sympathetic nervous system activity), and amygdala dependent modulation of defensive reflexes (fear potentiated startle). We expect that extinction learning is impaired in AD patients and will improve after exposure therapy. We hypothesize that extinction learning will improve to a greater degree after IPI than TAU. We expect that the response output measures are related to neural network activation (see P4). We expect extinction learning parameters being related to moderators of clinical outcome.

Furthermore, clinical anxiety is characterized by an incapacity (or reduced ability) to recognize both danger and safety signals and consequently to overestimate danger. The impaired recognition of danger signals prompts a continuous search for safety and a sustained feeling of apprehension. This symptomatology is well modelled by paradigms like contextual fear conditioning. In a context-conditioning paradigm the subjects cannot predict the aversive event (US) and consequently show a sustained fear response. Sustained fear is a long-lasting state of apprehension induced by the inability to identify the source of threat. As this technology is available at 4 sites (Dresden, Würzburg, Bochum, Marburg), we will here add a virtual reality (VR) paradigm to the assessments within P3 as an elegant and innovative tool to realize contextual fear conditioning in an ecological fashion in humans in analogy to animal models. By means of a VR context conditioning paradigm we are able to investigate the mechanisms underlying the acquisition and extinction of such sustained fear. Notably, we assess extinction learning on the cognitive (ratings), behavioral (startle responses and avoidance/approach) and physiological (skin conductance) level of responses. We expect extinction learning deficits in anxiety patients which will be improved after treatment.

Project P3 is essential for the identification of extinction learning being a mediator for outcome. Beyond it provides a range of experimental data regarding the mechanism of sustained fear and extinction in its role in AD. By applying two experimental paradigms covering sustained fear (VR) and extinction to all patients giving informed consent,

[figure not shown]
moderators of clinical outcome (e.g., type of AD, comorbidity, severity etc.) can be related to the mediating process. Moreover, by investigating the neural networks (P4) and (epi)genetic modulation (P5) of extinction learning we might provide evidence for central mediator and moderator mechanisms.

### 3.2 In- and exclusion criteria, recruitment strategy

**Patients.** Eligible patients from the RCT (P1) will be included in P3. Due to the startle procedure patients with severe hearing problems will be excluded from P3.

**Controls.** In conjunction with P4 we will recruit control subjects from the general population in the local area of the respective trial site. Controls will be matched for gender, age (+/- 5 years), education, handedness, and smoking. Inclusion criteria: 1) aged 15-70 years, 2) informed consent. Exclusion criteria: any lifetime psychiatric disorder according to DSM-5 criteria (excluding nicotine dependence); severe hearing problems; general medical contraindications (e.g. neurological or cardiovascular diseases).

Due to the shared experimental paradigms, patients and controls will participate in two experiments (the VR experiment and a fear conditioning procedure) in the psychophysiological lab on day 1, while extinction learning and reinstatement will be tested in the fMRI scanner on day 2. Those patients not eligible for fMRI will complete the extinction paradigm in the psychophysiological lab on day 2 (see Figure 2 for details).

**Figure 2.** Patient flow for experimental add-on study

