## 1. Evidence and study rationale

### 1.1 Extinction learning

A widely accepted view on the nature of extinction holds that extinction is conveyed by forming a second, inhibitory CS-US association in addition to the formerly acquired excitatory CS-US association (fear memory). Fear memories are thus not erased, but can be retrieved under certain circumstances. This phenomenon, also known as return of fear, clinically presents as a reoccurrence of anxiety symptoms or relapse. A great body of preclinical evidence has investigated the conditions under which return of fear can be observed and emphasises the key role of context variables during fear extinction. Context information is critically linked to the extinction memory and acts as a gating mechanism as to whether the fear memory is inhibited or not. From a neurobiological viewpoint, context information during extinction is stored in the hippocampus and fear inhibition is signalled by concerted action of the ventromedial prefrontal cortex, the amygdala and the hippocampus. Potential context variables do not only encompass external or internal states, but also temporal characteristics of the treatment. One prominent example is the spontaneous recovery of fear where the time between treatment and relapse can be interpreted as a gradually changing context, making it difficult to recall the original inhibitory memory trace in this seemingly new context. *In this view, the timing and spacing of exposure sessions (inter-trial intervals (ITI)) seems to be particular relevant and thus we focus this chapter on this topic.*

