### **2.2.8 Proposed sample size and power calculations**

Focusing on the HAM-A total score as the core primary outcome measure for determining the sample size, we expect - building on the meta-analytic results and pilot tests - that patients in IPI group will reduce the HAM-A-score (end of treatment) by 12 points. In the TAU group we expect a reduction by 10 points. Using a power of 80%, a test significance level of  $\alpha = 5\%$ , a standard deviation of 10 points and a one-sided t-test to detect differences between the IPI and TAU group, a total of 310 patients are needed per group. Based on previous such trials  drop-out rates during treatment including follow-up of 10%-15% are expected. Total n to be enrolled is 720 and to be analyzed 620.

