### 3.3 Experimental procedure

Extinction learning comprises different phases. First, the individual learns that a feared cue (or context) is no longer associated with the expected aversive outcome. With repeated extinction trials, extinction memory is consolidated and can be recalled even under stressful circumstances or in different contexts. Here we want to investigate fear conditioning and extinction learning in the laboratory. It is aimed to relate these multiple psychophysiological measures of extinction learning to neural network activation during extinction examined in P4, and its (epi)genetic modulation (see P5). We will use a delayed extinction paradigm, meaning that during day one subjects will learn that one cue (CS+ neutral face 1) is associated

with the aversive US (pulsed tactile electrostimulation on the forearm; 500ms in individually adjusted intensity reflecting “uncomfortable, but not painful” experiences) while the other cue (CS- neutral face 2) is never paired with the US. To ensure successful learning by all subjects (extinction learning can only be investigated in a meaningful way when the fear responses are reliably acquired) we will explicitly instruct all subjects that one of the two stimuli is followed by the US. To ensure successful conditioning subjective and physiological responses during acquisition were compared to responses during a short pre-conditioning phase (presenting CS+ and CS- alone for three times each) conducted immediately prior to conditioning. Duration of the task on day 1 is about 10 minutes (total duration of the assessment including electrode preparation, adjustment of electrostimulation, and expectancy ratings: 1h).

Extinction starts at day 2 with a reactivation of the fear memory (the CS+ followed by the US once). Then CS+ and CS- will be presented 20 times each without any US. Directly after extinction learning, fear will be reinstated by presenting the US alone (3X). Recall of extinction memory will then be tested by 10-CS-trial each. In order to maximize synergies between P3 and P4 and to minimize the load for included patients, the second part of the delayed extinction paradigm will be conducted within the MRI scanner as part of project in eligible subjects (Table 2).

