The VR context conditioning paradigm (delivered only at day 1) consists of six phases (exploration, two conditioning phases, a behavioral test, and two extinction phases) separated by verbal assessments. During the exploration phase, subjects explore each virtual office for 2 min by means of a joystick. During the two conditioning phases, subjects hear the desperate female scream (US) in one room (CTX+), but never in the other room (CTX-). Importantly, the US is presented unpredictably during the visit of the CTX+. A trial starts in a corridor (the inter-trial interval, ITI) and then subjects are passively guided into one virtual office. Each context (CTX+ and CTX-) is entered three times during the conditioning and extinction phases. For the behavioral test, participants are in the middle of the corridor and have to actively enter one virtual office. Subjects can make the choice by using a joystick. The extinction phases are similar the conditioning phases, except that no US is delivered. Startle-eliciting stimuli are delivered in each room as well as in the corridor. Duration of the task is approx. 1 h.

**Table 2.** Description of the delayed fear extinction and the VR context conditioning paradigms (shared paradigm P3 & P4)

	Day 1 (lab only)	Day 2 (fMRI; if not eligible: lab only)	
	Instructed fear conditioning	Fear extinction learning	Reinstatement test
VR paradigm:			
Conditioning phase:			
Frequency CTX+	12		
Frequency CTX-	12		
Frequency US	12		
Extinction phase:			
Frequency CTX+	20		
Frequency CTX-	20		
Conditioning & extinction paradigm:			
Frequency CS+	13	20	10

Frequency CS-	13	20	10
Frequency US	6	1	3 (CS/US)
Dependent variables:			
FPS recording	X	- (lab: X)	- (lab: X)
SC recording	X	X	X
HR recording	X	- (lab: X)	- (lab: X)
Expectancy ratings	X	X	X
Questionnaire on VR experiences	X		

FPS: fear potentiated startle; SC: skin conductance; HR: heart rate; Expectancy ratings: expectancy of US occurrence (0-100%); X: assessment; -: no assessment (technical restrictions in the MRI environment)

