### **3.5 Statistical analyses**

To test the effects of conditioning, extinction and reinstatement on startle blink magnitudes, skin conductance response, heart rate response, and expectancy ratings analyses of variance with repeated measurements are conducted with within-subjects factors of Phase (pre-conditioning vs. conditioning vs. extinction vs. reinstatement) and Cue (CS+ vs. CS-). To test the effect of interindividual differences between patients (e.g. primary diagnosis, severity, comorbidity, chronicity, depression) on test performance (e.g. intensity and speed of conditioning, extinction, and reinstatement) mixed models of variance or correlation analyses are conducted.

The statistical analysis for the contextual fear is similar to the above mentioned analyses. Namely, five separated analyses of variance with repeated measurements are calculated for each dependent variable (startle blink magnitude, skin conductance, hear rate response, anxiety and expectancy ratings). In parallel, the within-subjects factor phase (Conditioning 1, Conditioning 2, Extinction 1, Extinction 2) and context (CTX+, CTX-, ITI) are considered. In the same manner, the clinical diagnoses or interindividual differences are considered.

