
#### **4.2 In- and exclusion criteria, recruitment strategy**

Patients. Eligible patients from the RCT (P1) who have undergone P3 will be included in P4. Based on previous experience we estimate that approximately 40% (n = 300) patients from P1 will be included for P4. Additional MRI-related exclusion criteria apply: (1) ferromagnetic objects in the body that cannot be removed, (2) tattoos or permanent makeup in the face and neck area, (3) pregnancy, (4) self-report of lifetime history of neurological disorders, (5) general medical conditions that preclude from MRI assessment.

Controls. In conjunction with P4 we will recruit control subjects (n = 100) from the general population in the local area of the respective trial site. Controls will be matched for gender, age (+/- 5 years), education, handedness, and smoking. Inclusion criteria: 1) aged 15-70 years, 2) informed consent. Exclusion criteria: any lifetime psychiatric disorder according to DSM-5 criteria (excluding nicotine dependence). Additional MRI-related exclusion criteria: (1) ferromagnetic objects in the body that cannot be removed, (2) tattoos or permanent makeup in the face and neck area, (3) pregnancy, (4) self-report of lifetime history of neurological disorders, (5) general medical conditions that preclude from MRI assessment.

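### Day-2 cue extinction is tested in the scanner for some and in the lab for others: planned controls have no startle or heart-rate data there, and section 3.5 has no term for setting

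*Combined protocol and SAP*

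**What the plan says.** Section 3.2 has patients and controls conditioned in the psychophysiology lab on day 1, with extinction and reinstatement in the scanner on day 2. The exception reads: "Those patients not eligible for fMRI will complete the extinction paradigm in the psychophysiological lab on day 2". Section 3.3 and Table 2 word it more broadly. The former sends eligible subjects to the scanner, and the latter gives the lab to anyone not eligible.

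On day 2, Table 2 records skin conductance and expectancy in either setting. Startle and heart rate are marked for the lab only; the dash for the scanner means "no assessment (technical restrictions in the MRI environment").

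On numbers, section 4.2 says "we estimate that approximately 40% (n = 300) patients from P1 will be included for P4". It also holds the only planned number of controls, 100, together with MRI exclusions for them. Section 2.2.8 says "Total n to be enrolled is 720 and to be analyzed 620".

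On aims, section 3.1 says "We expect that extinction learning is impaired in AD patients and will improve after exposure therapy" and lists startle among the response levels to be assessed. Section 3.3 aims to "relate these multiple psychophysiological measures of extinction learning to neural network activation during extinction examined in P4".

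On analysis, section 3.5 applies repeated-measures ANOVA to startle, skin conductance, heart rate and expectancy, with "within-subjects factors of Phase (pre-conditioning vs. conditioning vs. extinction vs. reinstatement") and Cue. It then relates performance to differences between patients such as diagnosis, severity and comorbidity. For the cue paradigm it names neither a setting factor nor a patient-control factor.

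Section 1.1 says "Context information is critically linked to the extinction memory" and treats context as deciding whether fear is inhibited.

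**The concern.** Where a person is tested on day 2 depends on scanner eligibility, and it determines both which measures exist and the context in which fear is extinguished. Scanned subjects extinguish in a place other than the one where they were conditioned; lab-tested patients return to the same kind of place. On the protocol's own theory this could change the extinction response.

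Two things are at stake. First, some stated comparisons have no data: the patient-control difference in cue-extinction startle and heart rate, and the link between those measures and brain activation during extinction. Second, for skin conductance and expectancy, an analysis that pools settings mixes place of testing with the effect of interest. That applies to any pooled patient-control contrast. It also applies to the patient-only analyses of diagnosis or severity in section 3.5, if scanner eligibility or acceptance varies with those characteristics (an assumption; the documents give no figures on this).

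**Working it through.** **Inputs.** 720 patients enrolled (section 2.2.8); about 300 patients scanned, and 100 controls (section 4.2); measures by setting (Table 2); VR at 4 of 7 sites (section 3.1).

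**Step 1: the plan's own share.** 300/720 = 41.7%, which fits the stated figure of about 40% (exactly 40% of 720 is 288).

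**Step 2: patients tested in the lab on day 2.** If all 720 enter P3 and everyone not scanned is tested in the lab, 720 − 300 = 420, or 58.3%. P3 takes consenting patients without severe hearing problems and gives no number. With assumed participation f, the lab share is (720f − 300)/(720f):
- f = 0.9: 348/648 = 53.7%
- f = 0.8: 276/576 = 47.9%
- f = 0.7: 204/504 = 40.5%

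**Step 3: who has which day-2 data (section 3.2 as worded, full participation).**

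| Group | Setting | Startle, heart rate | Skin conductance, expectancy | fMRI |
|---|---|---|---|---|
| Patients, about 300 | scanner | no | yes | yes |
| Patients, up to 420 | lab | yes | yes | no |
| Controls, 100 | scanner | no | yes | yes |

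No group has startle or heart rate together with fMRI, and the control row has neither startle nor heart rate. A startle ANOVA over all four phases has no extinction or reinstatement cells for anyone scanned.

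**Step 4: size of the mixing.** Let s be the lab-minus-scanner difference in SD units. Pooled patients against scanner-tested controls are biased by (lab share) × s. With the 58.3% share, s = 0.2 gives 0.583 × 0.2 = 0.12 SD, and s = 0.5 gives 0.29 SD. Both values of s are assumed; the documents give none.

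**Step 5: price of matching on setting.** With equal variances, the ratio of standard errors, scanner-only to pooled, is

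sqrt(1/300 + 1/100) / sqrt(1/720 + 1/100) = 0.1155/0.1067 = 1.08.

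The detectable effect at 80% power and two-sided 5%, (1.960 + 0.842) × sqrt(1/n1 + 1/n2), is d = 0.32 for 300 vs 100, against d = 0.30 for 720 vs 100. With 70% participation (504 vs 100) the ratio falls to sqrt(0.01333/0.01198) = 1.05, so 8% is the upper end.

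**Step 6: what VR still offers.** Sections 3.2 to 3.4 have patients and controls do the VR task in the lab on day 1, with two extinction phases and 18 startle probes per phase. With subjects spread equally over sites and full participation (assumed), 720 × 4/7 = 411 patients and 100 × 4/7 = 57 controls; the detectable effect is about d = 0.40.

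**The case against.** A reader might infer that P3 cannot test impaired extinction on startle at all. The documents do not support that. The VR paradigm measures startle and heart rate during extinction, in both groups and in one setting. Section 3.1 states a patient deficit for it, and section 3.5 analyses its extinction phases. The gap concerns the day-2 cue paradigm only. VR runs at 4 sites and within a single day, so it does not replace delayed cue extinction or reinstatement, but it is a valid patient-control test.

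That every control is scanned is also an inference. The P3 control criteria in section 3.2 list no MRI exclusions, and section 3.3 and Table 2 could admit lab-tested controls. Figure 2, cited there for details, is not visible in the text reviewed. This stands as a reason to reconcile the passages. It does not close the gap, because no number of lab-tested controls is planned.

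It is also true that section 3.5 prescribes no pooled patient-control model, that day-1 contrasts share one setting, and that Table 2 openly states the MRI restriction. Section 4.1 already plans skin conductance and expectancy in scanned patients and controls, so the data for a matched contrast will exist. The criticism is therefore of silence: nothing commits the analysis to the matched contrast or to a setting term, and the choice could be made after seeing results.

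**Conclusion.** The point holds for day-2 cue extinction and reinstatement. As section 3.2 is worded, no control is planned to have startle or heart rate there, no subject has them together with fMRI, and the four-phase startle and heart-rate ANOVA can be run in full only in lab-tested patients. For skin conductance and expectancy, section 3.5 leaves setting unaddressed although section 1.1 gives a direct reason to expect it to matter.

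The lab share of 58% is an upper figure that rests on all 720 patients joining P3 and all unscanned patients being tested in the lab; at assumed participation of 70% to 90% it is 40% to 54%. The bias from pooling is that share times a setting effect of unknown size.

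It would be too strong to say that every patient-control contrast in P3 is confounded. Day-1 contrasts, including VR extinction, are not affected, and scanner-only contrasts on day 2 are available at little cost. The link to brain activation also survives for skin conductance and expectancy. The randomised IPI-TAU comparison of HAM-A is untouched.

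**What to change.** In section 3.5:

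1. Make patient-control contrasts of day-2 skin conductance and expectancy in scanner-tested patients against scanner-tested controls (about 300 vs 100).
2. Add day-2 setting, and its interaction with Phase, to every pooled patient analysis of the cue paradigm.
3. Limit day-2 startle and heart-rate analyses to lab-tested subjects, and base the patient-control test of startle extinction on the VR paradigm. Day-1 conditioning startle should not stand in for it, since it does not measure extinction.

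In sections 3.1 and 3.3, limit the link to brain activation during cue extinction to skin conductance and expectancy. Reconcile section 3.2, which gives the lab alternative to patients, with section 3.3 and Table 2, and state whether any controls will be tested in the lab on day 2 and how many.

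The cost is wording, a standard error up to about 8% larger in the day-2 patient-control contrasts of skin conductance and expectancy, and one narrowed aim. No new recruitment or procedure is needed.
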